***Systemic AE:***

Systemic AEs are all AEs that are not injection or administration site reactions. They therefore include systemic manifestations such as headache, fever, as well as localized or topical manifestations that are not associated with the vaccination or administration site (eg, erythema that is localized but that is not occurring at the injection site).

***Adverse Event of Special Interest (AESI):***

An adverse event of special interest is one of scientific and medical concern specific to the Sponsor’s product or program, for which ongoing monitoring and rapid communication by the investigator to the sponsor can be appropriate. Such an event might warrant further investigation in order to characterize and understand it. Depending on the nature of the event, rapid communication by the study Sponsor to other parties (eg, regulators) might also be warranted.

### 9.1.2 Safety Endpoints

The endpoints for the evaluation of safety are:

- Occurrence, nature (Medical Dictionary for Regulatory Activities [MedDRA] preferred term [PT]), duration, intensity, and relationship to vaccination of any unsolicited systemic AEs reported in the 30 minutes after each vaccination.
- Occurrence, time to onset, number of days of occurrence, intensity, action taken, and whether the reaction led to early termination from the study, of solicited (prelisted in the subject's diary card and CRB) injection site reactions and systemic reactions occurring up to 7 days after each vaccination.
- Occurrence, nature (MedDRA system organ class [SOC] and PT), time to onset, duration, intensity, relationship to vaccination (for systemic AEs only), and whether the event led to early termination from the study, of unsolicited AEs up to 28 days after each vaccination.
- Occurrence, nature (MedDRA SOC and PT), time to onset, seriousness criteria, relationship to vaccination, outcome, and whether the event led to early termination from the study, of SAEs (including AESIs) throughout the study.
- Occurrence, nature (MedDRA PT), time to onset, and relationship to vaccination of AESIs throughout the study.

### 9.1.3 Safety Assessment Methods

At V01, the Investigator or a delegate will perform a clinical or medically-driven physical examination.

At V03 (D28 [+7 days]), and / or V05, as applicable, the Investigator or a delegate may perform a targeted clinical or medically-driven physical examination, as necessary, and will ask the subject / parent / guardian about any solicited reactions and unsolicited AEs recorded in the diary card, as well as about any other AEs that may have occurred since the previous visit.

All relevant data will be transcribed into the CRB according to the instructions provided by the Sponsor.

#### 9.1.3.1 Immediate Post-vaccination Observation Period

Subjects will be kept under observation for 30 minutes after each vaccination to ensure their safety. The post-vaccination observation should be documented in the source document. Any AE that occurs during this period will be noted on the source document and recorded in the CRB, as follows:

- Unsolicited systemic AEs will be recorded as immediate AEs in the CRB (presence marked as "yes" and details collected).
- Solicited and unsolicited injection site reactions and solicited systemic reactions will be recorded in the CRB in the same way as any reactions starting on the day of vaccination.

- SAEs will be recorded in the CRB and reported to the Sponsor in the same way as any other SAEs, according to the procedures described in [Section 10](#).

#### **9.1.3.2 Reactogenicity (Solicited Reactions From Day 0 to Day 7 After Each Vaccination)**

After each vaccination, subjects / parents / guardians will be provided with a diary card, a digital thermometer, and a flexible ruler, and will be instructed how to use them. The following items will be recorded by the subjects in the diary card on the day of vaccination and for the next 7 days (ie, D0 to D7) until resolution:

- Daily temperature, with the route by which it was taken
- Daily measurement or intensity grade of all other solicited injection site and systemic reactions
- Action taken for each event (eg, medication)

The action(s) taken by the subject / parent / guardian to treat and/or manage any **solicited reactions** will be classified in the CRB using the following list (all applicable items should be checked):

- None
- Medication
- Health care provider contact
- Hospitalized
- Discontinuation of study vaccination

[Table 9.1](#), [Table 9.2](#), [Table 9.3](#), [Table 9.4](#), and [Table 9.5](#) present, respectively, the injection site reactions and systemic reactions that are prelisted in the diary cards and CRB, together with the intensity scales.

**Table 9.1: Solicited injection site reactions for infants and toddlers aged < 36 months: terminology, definitions, and intensity scales**

CRB term (MedDRA LLT)	Injection site tenderness	Injection site erythema	Injection site swelling	Injection site induration	Injection site bruising
MedDRA PT	Injection site pain	Injection site erythema	Injection site swelling	Injection site induration	Injection site bruising
Diary card term	Tenderness	Redness	Swelling	Hardening	Bruising
Definition	Pain when the injection site is touched or injected limb mobilized	Presence of a redness including the approximate point of needle entry	Swelling at or near the injection site Swelling or edema is caused by a fluid infiltration in tissue or cavity and, depending on the space available for the fluid to disperse, swelling may be either soft (typically) or firm (less typical) to touch and thus can be best described by looking at the size of the swelling	Hardening at or near the injection site. Hardening is caused by a slow diffusion of the product in the tissue leading to a thick or hard area to touch at or near the injection site and thus can be best described by looking at the size of the hardening.	Bruising is the result of the diffusion of blood in the skin from ruptured blood vessels that forms a purple or black and blue spot on the skin. It can be best described by looking at its size.
Intensity scale*	Grade 1: Minor reaction when injection site is touched  Grade 2: Cries or protests when injection site is touched  Grade 3: Cries when injected limb is mobilized, or the movement of the injected limb is reduced	Grade 1: > 0 to < 25 mm  Grade 2: ≥ 25 to < 50 mm  Grade 3: ≥ 50 mm	Grade 1: > 0 to < 25 mm  Grade 2: ≥ 25 to < 50 mm  Grade 3: ≥ 50 mm	Grade 1: > 0 to < 25 mm  Grade 2: ≥ 25 to < 50 mm  Grade 3: ≥ 50 mm	Grade 1: > 0 to < 25 mm  Grade 2: ≥ 25 to < 50 mm  Grade 3: ≥ 50 mm

\* For the subjective reaction of tenderness, parents / guardians will record the intensity level (Grade 1, 2, or 3) in the diary card. For the measurable reactions of redness, swelling, hardening, and bruising, they will record just the size of the reaction, and the classification as Grade 1, 2, or 3 will be assigned at the time of the statistical analysis.

**Table 9.2: Solicited injection site reactions for children aged 3 to 11 years: terminology, definitions, and intensity scales**

CRB term (MedDRA LLT)	Injection site pain	Injection site erythema	Injection site swelling	Injection site induration	Injection site bruising
MedDRA PT	Injection site pain	Injection site erythema	Injection site swelling	Injection site induration	Injection site bruising
Diary card term	Pain	Redness	Swelling	Hardening	Bruising
Definition	Pain either present spontaneously or when the injection site is touched or injected limb is mobilized	Presence of a redness including the approximate point of needle entry	Swelling at or near the injection site  Swelling or edema is caused by a fluid infiltration in tissue or cavity and, depending on the space available for the fluid to disperse, swelling may be either soft (typically) or firm (less typical) to touch and thus can be best described by looking at the size of the swelling	Hardening at or near the injection site.  Hardening is caused by a slow diffusion of the product in the tissue leading to a thick or hard area to touch at or near the injection site and thus can be best described by looking at the size of the hardening.	Bruising is the result of the diffusion of blood in the skin from ruptured blood vessels that forms a purple or black and blue spot on the skin. It can be best described by looking at its size.

Intensity scale*	Grade 1: Easily tolerated Grade 2: Sufficiently discomforting to interfere with normal behavior or activities Grade 3: Incapacitating, unable to perform usual activities	Grade 1: > 0 to < 25 mm Grade 2: ≥ 25 to < 50 mm Grade 3: ≥ 50 mm	Grade 1: > 0 to < 25 mm Grade 2: ≥ 25 to < 50 mm Grade 3: ≥ 50 mm	Grade 1: > 0 to < 25 mm Grade 2: ≥ 25 to < 50 mm Grade 3: ≥ 50 mm	Grade 1: > 0 to < 25 mm Grade 2: ≥ 25 to < 50 mm Grade 3: ≥ 50 mm
-------------------------	---	---	---	---	---

\* For the subjective reaction of pain, parents / guardians will record the intensity level (Grade 1, 2, or 3) in the diary card. For the measurable reactions of redness, swelling, hardening, and bruising, they will record just the size of the reaction, and the classification as Grade 1, 2, or 3 will be assigned at the time of the statistical analysis.

**Table 9.3: Solicited injection site reactions for children aged 12 to 17 years: terminology, definitions, and intensity scales**

CRB term (MedDRA LLT)	Injection site pain	Injection site erythema	Injection site swelling	Injection site induration	Injection site bruising
MedDRA PT	Injection site pain	Injection site erythema	Injection site swelling	Injection site induration	Injection site bruising
Diary card term	Pain	Redness	Swelling	Hardening	Bruising
Definition	Pain either present spontaneously or when the injection site is touched or injected limb is mobilized	Presence of a redness including the approximate point of needle entry	Swelling at or near the injection site  Swelling or edema is caused by a fluid infiltration in tissue or cavity and, depending on the space available for the fluid to disperse, swelling may be either soft (typically) or firm (less typical) to touch and thus can be best described by looking at the size of the swelling	Hardening at or near the injection site.  Hardening is caused by a slow diffusion of the product in the tissue leading to a thick or hard area to touch at or near the injection site and thus can be best described by looking at the size of the hardening.	Bruising is the result of the diffusion of blood in the skin from ruptured blood vessels that forms a purple or black and blue spot on the skin. It can be best described by looking at its size.

Intensity scale*	Grade 1: A type of adverse event that is usually transient and may require only minimal treatment or therapeutic intervention. The event does not generally interfere with usual activities of daily living.  Grade 2: A type of adverse event that is usually alleviated with additional therapeutic intervention. The event interferes with usual activities of daily living, causing discomfort but poses no significant or permanent risk of harm to the research participant.  Grade 3: A type of adverse event that interrupts usual activities of daily living, or significantly affects clinical status, or may require intensive therapeutic intervention.	Grade 1: $\geq 25$ to $\leq 50$ mm  Grade 2: $\geq 51$ to $\leq 100$ mm  Grade 3: $> 100$ mm	Grade 1: $\geq 25$ to $\leq 50$ mm  Grade 2: $\geq 51$ to $\leq 100$ mm  Grade 3: $> 100$ mm	Grade 1: $\geq 25$ to $\leq 50$ mm  Grade 2: $\geq 51$ to $\leq 100$ mm  Grade 3: $> 100$ mm	Grade 1: $\geq 25$ to $\leq 50$ mm  Grade 2: $\geq 51$ to $\leq 100$ mm  Grade 3: $> 100$ mm
-------------------------	---	--	--	--	--

\* For the subjective reaction of pain, subjects / parents / guardians will record the intensity level (Grade 1, 2, or 3) in the diary card. For the measurable reactions of redness, swelling, hardening, and bruising they will record just the size of the reaction, and the classification as Grade 1, 2, or 3 will be assigned at the time of the statistical analysis

**Table 9.4: Solicited systemic reactions for infants and toddlers aged < 36 months: terminology, definitions, and intensity scales**

CRB term (MedDRA LLT)	Fever	Vomiting	Crying abnormal	Drowsiness	Appetite lost	Irritability
MedDRA PT	Pyrexia	Vomiting	Crying	Somnolence	Decreased appetite	Irritability
Diary card term	Temperature	Vomiting	Abnormal crying	Drowsiness	Loss of appetite	Irritability
Definition	Elevation of temperature to $\geq 38.0^{\circ}\text{C}$ ( $\geq 100.4^{\circ}\text{F}$ )	Vomiting does not include spitting up	Inconsolable crying without a determined reason	Reduced interest in surroundings, or increased sleeping	See intensity scale	An excessive response to stimuli: increased fussiness, whining, and fretfulness despite attempts to comfort the infant and despite caregiver responses that would normally be soothing
Intensity scale*	Grade 1: $\geq 38.0^{\circ}\text{C}$ to $\leq 38.5^{\circ}\text{C}$ or $\geq 100.4^{\circ}\text{F}$ to $\leq 101.3^{\circ}\text{F}$ Grade 2: $> 38.5^{\circ}\text{C}$ to $\leq 39.5^{\circ}\text{C}$ or $> 101.3^{\circ}\text{F}$ to $\leq 103.1^{\circ}\text{F}$ Grade 3: $> 39.5^{\circ}\text{C}$ or $> 103.1^{\circ}\text{F}$	Grade 1: 1 episode per 24 hours  Grade 2: 2–5 episodes per 24 hours  Grade 3: $\geq 6$ episodes per 24 hours or requiring parenteral hydration	Grade 1: < 1 hour  Grade 2: 1–3 hours  Grade 3: > 3 hours	Grade 1: Sleepier than usual or less interested in surroundings  Grade 2: Not interested in surroundings or did not wake up for a feed / meal  Grade 3: Sleeping most of the time or difficult to wake up	Grade 1: Eating less than normal  Grade 2: Missed 1 or 2 feeds / meals completely  Grade 3: Refuses $\geq 3$ feeds / meals or refuses most feeds / meals	Grade 1: Easily consolable  Grade 2: Requiring increased attention  Grade 3: Inconsolable

\* For all reactions but fever, parents / guardians will record the intensity level (Grade 1, 2, or 3) in the diary card. For fever, they will record the body temperature, and the classification as Grade 1, 2, or 3 will be assigned at the time of the statistical analysis based on the unit used to measure the temperature and the intensity scale.

**Table 9.5: Solicited systemic reactions for children aged 3 to 17 years: terminology, definitions, and intensity scales**

CRB term (MedDRA LLT)	Fever	Headache	Malaise	Myalgia	Shivering
MedDRA PT	Pyrexia	Headache	Malaise	Myalgia	Chills
Diary card term	Temperature	Headache	Feeling unwell	Muscle aches and pains	Chills
Definition	Elevation of temperature to $\geq 38.0^{\circ}\text{C}$ ( $\geq 100.4^{\circ}\text{F}$ )	Pain or discomfort in the head or scalp. Does not include migraine.	General ill feeling. Malaise is a generalized feeling of discomfort, illness, or lack of well-being that can be associated with a disease state. It can be accompanied by a sensation of exhaustion or inadequate energy to accomplish usual activities.	Muscle aches and pains are common and can involve more than one muscle at the same time. Muscle pain can also involve the soft tissues that surround muscles. These structures, which are often referred to as connective tissues, include ligaments, tendons, and fascia (thick bands of tendons).  Does not apply to muscle pain at the injection site which should be reported as injection site pain.	Cold feeling.
Intensity scale*	Grade 1: $\geq 38.0^{\circ}\text{C}$ to $\leq 38.4^{\circ}\text{C}$ , or $\geq 100.4^{\circ}\text{F}$ to $\leq 101.1^{\circ}\text{F}$	Grade 1: A type of AE that is usually transient and may require only minimal treatment or therapeutic intervention. The event does not generally interfere with usual activities of daily living.	Grade 1: A type of AE that is usually transient and may require only minimal treatment or therapeutic intervention. The event does not generally interfere with usual activities of daily living.	Grade 1: A type of AE that is usually transient and may require only minimal treatment or therapeutic intervention. The event does not generally interfere with usual activities of daily living.	Grade 1: A type of AE that is usually transient and may require only minimal treatment or therapeutic intervention. The event does not generally interfere with usual activities of daily living.

	Grade 2: $\geq 38.5^{\circ}\text{C}$ to $\leq 38.9^{\circ}\text{C}$ , or $\geq 101.2^{\circ}\text{F}$ to $\leq 102.0^{\circ}\text{F}$	Grade 2: A type of AE that is usually alleviated with additional therapeutic intervention. The event interferes with usual activities of daily living, causing discomfort but poses no significant or permanent risk of harm to the research participant.	Grade 2: A type of AE that is usually alleviated with additional therapeutic intervention. The event interferes with usual activities of daily living, causing discomfort but poses no significant or permanent risk of harm to the research participant.	Grade 2: A type of AE that is usually alleviated with additional therapeutic intervention. The event interferes with usual activities of daily living, causing discomfort but poses no significant or permanent risk of harm to the research participant.	Grade 2: A type of AE that is usually alleviated with additional therapeutic intervention. The event interferes with usual activities of daily living, causing discomfort but poses no significant or permanent risk of harm to the research participant.
	Grade 3: $\geq 39.0^{\circ}\text{C}$ or $\geq 102.1^{\circ}\text{F}$	Grade 3: A type of AE that interrupts usual activities of daily living, or significantly affects clinical status, or may require intensive therapeutic intervention.	Grade 3: A type of AE that interrupts usual activities of daily living, or significantly affects clinical status, or may require intensive therapeutic intervention.	Grade 3: A type of AE that interrupts usual activities of daily living, or significantly affects clinical status, or may require intensive therapeutic intervention.	Grade 3: A type of AE that interrupts usual activities of daily living, or significantly affects clinical status, or may require intensive therapeutic intervention.

\* For all reactions but fever, subjects / parents / guardians will record the intensity level (Grade 1, 2, or 3) in the diary card. For fever, they will record the body temperature, and the classification as Grade 1, 2, or 3 will be assigned at the time of the statistical analysis based on the unit used to measure the temperature and the intensity scale.

***Important notes for the accurate assessment of temperature:***

Subjects / parents / guardians are to measure body temperature once per day, preferably always at the same time. The optimal time for measurement is the evening, when body temperature is the highest. Temperature is also to be measured at the time of any apparent fever. The observed daily temperature and the route of measurement are to be recorded in the diary card, and the highest temperature will be recorded by the site in the CRB. The preferred route for this study is rectal for subjects 6 months to < 4 years of age and oral for subjects 4 years of age and older. However, axillary is also acceptable for subjects 6 months of age and older if unable to obtain the preferred route of measurement. Pre-vaccination temperature is also systematically collected by the investigator on the source document. Tympanic thermometers must not be used.

#### **9.1.3.3 Unsolicited Adverse Events**

In addition to recording solicited reactions, subjects / parents / guardians will be instructed to record any other medical events that may occur during the 28-day period after each vaccination. Space will be provided in the diary card for this purpose.

Information on SAEs will be collected and assessed throughout the study, from inclusion until 6 months after the last vaccination. Any SAE occurring at any time during the study will be reported by the Investigator in the CRB according to the completion instructions provided by the Sponsor; this includes checking the “Serious” box on the AE CRF and completing the appropriate Death/Safety Complementary Information CRFs. All information concerning the SAE is to be reported either as part of the initial reporting or during follow-up reporting if relevant information became available later (eg, outcome, medical history, results of investigations, copy of hospitalization reports). In case a subject experiences febrile convolution (neurological event associating fever and seizure), the assessment will be performed according to the “Guideline for definition and collection of cases of febrile convolution”, and this event will be considered an SAE. See [Section 10](#) for further details on SAE reporting.

For each unsolicited AE (whether serious or non-serious), the following information is to be recorded:

- Start and stop datesa
- Intensity of the event:

For measurable unsolicited AEs that are part of the list of solicited reactions, the size of the AE as well as the temperature for fever will be collected and analyzed based on the corresponding scale used for solicited reactions (see [Table 9.1](#), [Table 9.2](#), [Table 9.3](#), [Table 9.4](#), and [Table 9.5](#)).

All other unsolicited AEs will be classified according to the following intensity scale:

---

a The stop date of all related AEs will be actively solicited. For other events, the investigator will provide the stop date when it becomes available. AEs for which no stop date was obtained during the course of the study will be considered as ongoing at the end of the study.

- Grade 1: A type of AE that is usually transient and may require only minimal treatment or therapeutic intervention. The event does not generally interfere with usual activities of daily living.
- Grade 2: A type of AE that is usually alleviated with additional therapeutic intervention. The event interferes with usual activities of daily living, causing discomfort but poses no significant or permanent risk of harm to the research participant.
- Grade 3: A type of AE that interrupts usual activities of daily living, or significantly affects clinical status, or may require intensive therapeutic intervention.
- Whether the AE was related to the investigational product (for unsolicited systemic AEs)  
The Investigator will assess the causal relationship between the AE and the investigational product as either “Not related” or “Related”, as described in [Section 9.1.3.5](#).
- Action taken for each AE (eg, medication)  
The action(s) taken by the subject / parent / guardian to treat and/or manage any unsolicited AEs will be classified in the CRB using the following list (all applicable items should be checked):
  - None
  - Medication
  - Health care provider contact
  - Hospitalized
  - Discontinuation of study vaccination
- Whether the AE was serious  
For each SAE, the investigator will complete all seriousness criteria that apply (outcome, elapsed time, and relationship to study procedures)
- Whether the AE caused study discontinuation

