4.4.1.2.5 Duration

Duration is derived from the start and stop dates of the unsolicited non-serious AE provided in the clinical database:

- Stop date of unsolicited non-serious AE - start date of unsolicited non-serious AE + 1.

The duration should be considered as missing only if one or both of the start and stop dates of the unsolicited non-serious AE is missing or partially missing.

Duration will be displayed by period as following:

- 1-3 days

- 4-7 days
- 8-14 days
- ≥ 15 days
- Missing

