4.4.1.3.3 Duration

Duration will be computed using the same methodology as for unsolicited non-serious AEs described in [Section 4.4.1.2.5](#).

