5.3.1.5 Start Date and Stop Date

Missing or partially missing start dates for unsolicited AEs will remain missing and will not be imputed. If either the start or stop date is missing or partially missing, the time of onset will be considered to be missing. Nevertheless unsolicited AEs with missing time of onset will be included in analyses according to the visit collected.

Missing or partially missing stop dates for AEs (solicited reactions and unsolicited AEs) will remain missing and will not be imputed.

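### The SAP does not carry forward the protocol's rule that an adverse event with no stop date is ongoing: it reports the duration, and in one section the onset, as missing

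*Protocol*

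**What the plan says.** Duration is a listed attribute of unsolicited AEs in protocol 9.1.2 ("time to onset, duration, intensity, relationship to vaccination (for systemic AEs only"). The study-long SAE and AESI endpoints in the same section do not list duration; the SAE endpoint lists outcome.

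Footnote a to protocol 9.1.3.3 sets out how stop dates are obtained. For related events: "The stop date of all related AEs will be actively solicited". For the rest: "For other events, the investigator will provide the stop date when it becomes available". It then gives a convention: "AEs for which no stop date was obtained during the course of the study will be considered as ongoing" at the end of the study.

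The SAP treats the same events as follows.

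- **4.4.1.2.5 (non-serious AEs):** duration is stop date minus start date plus 1. On incomplete dates it says "The duration should be considered as missing only if one or both of the start and stop dates" is missing or partial. The display categories are 1-3, 4-7, 8-14 and at least 15 days, plus Missing.
- **4.4.1.3.3 (SAEs):** "Duration will be computed using the same methodology as for unsolicited non-serious AEs".
- **5.3.1.5:** "Missing or partially missing stop dates for AEs (solicited reactions and unsolicited AEs) will remain missing and will not be imputed". It also makes time of onset missing if either the start or the stop date is incomplete.
- **4.4.1.2.4:** time of onset is start date minus vaccination date, and is missing only if one of those two dates is incomplete.

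The SAP derives an ongoing status for solicited reactions (4.4.1.1.7) but has none for unsolicited AEs or SAEs.

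**The concern.** The protocol gives an event with no stop date a meaning: it had not ended. The SAP gives it none. An unresolved condition and a record with an unusable date fall in the same Missing row, so a reader of the duration table cannot see how many events were open.

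The loss matters most for related AEs. Their stop dates are actively sought, and protocol 5.1.4 has related AEs followed until they resolve, stabilise or become chronic. A blank stop date for a related AE therefore points towards non-resolution. Protocol 5.1.2 describes this as the first use of QIV-HD in children, and persistent events are the part of a duration table that a safety reader looks for.

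The onset rule in 5.3.1.5 makes this worse. An event with a known start date loses its onset day merely because it has not ended. SAP 4.4.1.2.4 counts non-serious AEs with missing onset as within 28 days, and 4.4.1.3.2 applies the same method to SAEs. If 5.3.1.5 governs, a late unresolved SAE could be counted in the 28-day post-dose period.

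**Working it through.** The plan states no figure on this point, so there is none to reproduce. The check applies the SAP's own formula to the planned days and then bounds the effect on the table.

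**1. The rules side by side, for an event with a complete start date and no stop date**

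| Item | Protocol 9.1.3.3 | SAP 4.4.1.2.5 / 4.4.1.3.3 | SAP 4.4.1.2.4 | SAP 5.3.1.5 |
|---|---|---|---|---|
| Status | Ongoing | None assigned | - | - |
| Duration | No value given | Missing | - | Stop date stays missing |
| Time of onset | - | - | Known | Missing |

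The SAP omits the status, and its two onset rules disagree with each other.

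**2. Bound on the row for 15 days or more**

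Let N be all AEs, k those with a known duration of at least 15 days, and m those with no stop date. The table shows k/N. The true share lies between k/N and (k+m)/N, so the shortfall is at most m/N, which cannot exceed the displayed Missing row.

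The documents give no counts. Assume N = 100 and k = 5:

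| m | Shown, 15 days or more | Missing row | Largest possible true share | Shown share if Missing leaves the denominator |
|---|---|---|---|---|
| 2 | 5% | 2% | 7/100 = 7% | 5/98 = 5.1% |
| 5 | 5% | 5% | 10/100 = 10% | 5/95 = 5.3% |
| 10 | 5% | 10% | 15/100 = 15% | 5/90 = 5.6% |
| 20 | 5% | 20% | 25/100 = 25% | 5/80 = 6.25% |

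While Missing stays in the denominator, the three shorter bands are not inflated. The SAP shows Missing as a category but does not state the denominator.

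**3. Must every such event have lasted at least 15 days?**

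Inputs: analysed non-serious AEs start on days 0 to 28 after a dose (SAP 4.4.1.2.4). They are collected to V03 or V05, nominally D28 or D56 (protocol 5.1.3). The last call is at about D180 for one dose or D208 for two (protocol synopsis).

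- Cut-off at the 6-month call: the latest onset gives 180 - 28 + 1 = 153 days, or 208 - 56 + 1 = 153 days after dose 2. All would qualify.
- Cut-off at V03 on D28: onset on D14 gives 28 - 14 + 1 = 15 days and D15 gives 14, so onsets on D15 to D28 do not qualify.
- Cut-off at V03 on D35, the end of its window: onset on D21 gives 35 - 21 + 1 = 15 days and D22 gives 14, so onsets on D22 to D28 do not qualify.
- SAE with the call at D180: onset on D166 gives 15 days and D167 gives 14, so onsets on D167 to D180 do not qualify.

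For non-serious AEs the first cut-off is not supported by the data collection. The 6-month call asks about SAEs and AESIs (protocol 5.1.4 and 11.1), so no planned contact shows that an unrelated non-serious AE open at V03 or V05 was still present at six months.

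**The case against.** The strongest defence is that the documents do not conflict. The footnote assigns a status and gives no duration, and protocol 12.3.1 says that missing safety data are not replaced and are shown as missing in the listings. The SAP follows that. The Missing row is displayed, so nothing is concealed. For SAEs, outcome is an endpoint and is summarised as collected (SAP 4.4.1.4.3). No decision rule uses AE duration, the early safety review criteria do not refer to it, and the study is descriptive.

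Most of this stands. It rules out the stronger reading that a reader might infer: that the SAP contradicts the protocol, that the longest-lasting events drop out of the table, and that durations are biased towards short ones. The events remain in a visible row, and the short bands rise only if Missing is removed from the denominator. A blank stop date also does not identify a long event: stop dates of unrelated AEs are supplied only as they become available, so a brief, resolved AE can lack one.

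The defence does not answer two things. Showing a status that the protocol already assigns replaces no date, so 12.3.1 does not prevent it. And the disagreement between SAP 4.4.1.2.4 and 5.3.1.5 on onset is internal to the SAP.

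**Conclusion.** The point holds as a reporting gap of limited size. The SAP does not implement the protocol's ongoing convention, unresolved events cannot be separated from events with unusable dates, and 5.3.1.5 removes a known onset day. The understatement of the row for 15 days or more cannot exceed the Missing row. In the illustration it is at most 2 to 20 percentage points, and that range rests wholly on assumed counts.

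A reader might go further and conclude that every event without a stop date belongs in the row for 15 days or more, with a minimum of 153 days. The documents do not support this. The figure needs follow-up to the 6-month call, which for non-serious AEs is not planned, and it fails for late-starting SAEs. Moving all such events would replace a visible unknown with a possible overstatement. The consequence for SAEs is smaller on duration, which is not a listed SAE endpoint, but the onset conflict applies to them as well.

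**What to change.** 1. In SAP 4.4.1.2.5, and so in 4.4.1.3.3, tabulate events with a complete start date and no stop date in their own row, labelled 'Ongoing at end of study (no stop date obtained)'. Keep Missing for missing or partial start dates and for partial stop dates. State the denominator and keep every row in it.
2. In SAP 5.3.1.5, remove the stop date from the time-of-onset rule so that it matches 4.4.1.2.4.
3. Do not move these events as a block into 15 days or more. If a minimum duration is wanted, give it as a supplement and run it only to the last contact at which that type of event was assessed: V03 or V05 for non-serious AEs, the 6-month call for SAEs.

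The cost is a few lines of SAP text and one derivation, with no new data. The row is defined by the absent date, so it needs no separate resolution field, which protocol 9.1.3.3 does not list for non-serious AEs. The downside is small: some unrelated AEs that resolved without a recorded date will appear as ongoing, which is what the protocol's convention already implies.
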